#### 5.0 Therapy required

1= No 2= Yes

#### 6.0 Outcome

1= resolved 2= improved 3= unchanged 4= worse

# Appendix V

# Adverse event form Day 2 Surveillance after Primary vaccination

1.0 Completeness of dosing. Amount ingested: 1=100%  $2=\ge 90\%$  3=<90%

#### 2.0 LOCAL REACTION

| Parameters               |                                   |
|--------------------------|-----------------------------------|
| Abdominal pain           | 1= No 2=Mild 3= moderate 4=severe |
| Cramp                    | 1= No 2= Yes                      |
| Distension               | 1=No 2= moderate 3= severe        |
| Vomiting                 | 1=No 2= Yes                       |
|                          |                                   |
| If yes, number/day       |                            |
| Other symptoms           | 1=No 2= Yes                       |
| *Diarrhoea [watery stool |                                   |
| or loose stool ]         |                                   |
| If yes above number/day  |                                   |
| (>3)                     |                                   |

\*Diarrhoea defined as passing of ≥ 3 loose or liquid stools per day

#### 3.0 SYSTEMIC REACTION

| Parameters   |              |
|--|--------------|
| Fever (oral or rectal temp>37.8°C If yes, temperature (°C) | 1= No 2= Yes |
| Loss of appetite/ Poor feeding                             | 1= No 2= Yes |
| Irritability   | 1= No 2= Yes |
| Nausea   | 1= No 2= Yes |
| Dizziness  | 1= No 2= Yes |
| Exanthema  | 1= No 2= Yes |
| Other  | 1= No 2= Yes |

#### 4.0 Relation to vaccine

1= None 2= Possible 3= Probable 4= Highly probable

## 5.0 Therapy required

1= No 2= Yes

#### 6.0 Outcome

1= resolved 2= improved 3= unchanged 4= worse

#### Appendix V

# Adverse event form Day 3 Surveillance after Primary vaccination

1.0 Completeness of dosing. Amount ingested: 1=100% 2=≥ 90% 3=<90%

#### 2.0 LOCAL REACTION

| 2.0 2001121011011        | · · · · · · · · · · · · · · · · · · · |
|--------------------------|---------------------------------------|
| Parameters               |                                       |
| Abdominal pain           | 1= No 2=Mild 3= moderate 4=severe     |
| Cramp                    | 1= No 2= Yes                          |
| Distension               | 1=No 2= moderate 3= severe            |
| Vomiting                 | 1=No 2= Yes                           |
| _                        |                                       |
| If yes, number/day       |                                       |
| Other symptoms           | 1=No 2= Yes                           |
| *Diarrhoea [watery stool |                                       |
| or loose stool ]         |                                       |
| If yes above number/day  |                                       |
| (>3)                     |                                       |

\*Diarrhoea defined as passing of ≥ 3 loose or liquid stools per day

#### 3.0 SYSTEMIC REACTION

| Parameters                        |              |
|-----------------------------------|--------------|
| Fever (oral or rectal temp>37.8°C | 1= No 2= Yes |
| If yes, temperature (°C)          |              |
| Loss of appetite/ Poor            | 1= No 2= Yes |
| feeding                           |              |
| Irritability                      | 1= No 2= Yes |
| Nausea                            | 1= No 2= Yes |
| Dizziness                         | 1= No 2= Yes |
| Exanthema                         | 1= No 2= Yes |
| Other                             | 1= No 2= Yes |

#### 4.0 Relation to vaccine

1= None 2= Possible 3= Probable 4= Highly probable

#### 5.0 Therapy required

1= No 2= Yes

#### 6.0 Outcome

| rincipal Investigator: Last, first, middle |  |
|--|--|
|  |  |

#### **AppendixV**

## Adverse event form Surveillance after Secondary vaccination

#### Day 1

1.0 Completeness of dosing. Amount ingested: 1=100%  $2=\ge 90\%$  3=<90%

#### 2.0 LOCAL REACTION

| Parameters  |                                   |
|---|-----------------------------------|
| Abdominal pain  | 1= No 2=Mild 3= moderate 4=severe |
| Cramp   | 1= No 2= Yes                      |
| Distension  | 1=No 2= moderate 3= severe        |
| Vomiting  | 1=No 2= Yes                       |
| If yes, number/day                                      |                                   |
| Other symptoms *Diarrhoea [watery stool or loose stool] | 1=No 2= Yes                       |
| If yes above number/day (> 3)                           |                                   |

\*Diarrhoea defined as passing of ≥ 3 loose or liquid stools per day

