#### Selection of study subjects

Before entering into the study children in the different age groups will be screened from the slums and history recorded (Appendix III). Although 158 children need to be recruited in the two age groups, more will be screened to obtain study subjects which meet the inclusion criteria. Previous experience in similar studies (Protocol No.98-001) has shown that around 30 to 40% more have to be screened. The children will be carefully examined by a physician. A detailed history of the volunteer of previous immunizations, nutritional status, recent illness (as outlined below) that can compromise the immune system, family background etc. will be taken (Appendix III). Healthy male and female children will be recruited from the urban slums.

Children will be excluded from enrollment if interviewers find: (a) a history of chronic gastrointestinal disorder, (b) diarrhoeal illness in the past 2 weeks (diarrhoea being defined as passing of  $\geq$  3 loose or liquid stools in 24 hours (c) febrile illness in the preceding week, or (d) other serious chronic illness (e) had antibiotic treatment at least 7 days prior to the enrollment in the study (f) children suffering from second or third degree of protein energy malnutrition (PEM).

A routine stool microscopic examination and culture for common enteric pathogens including ETEC will be carried out three days prior to vaccination. Children whose stools are postive for ETEC will not be vaccinated since this will interfere in the evaluation of the response to the vaccine When immunization for the second dose of the vaccine will be carried out (14 days after the first dose) children who have fever or diarrhoea will be excluded from the study.

The nutritional level of the children will be monitored using anthropometric measurements (weight-for-age, and weight-for-length/height). Children below > -2SD of the NCHS will not be enrolled. We plan to recruit children in the 6 month -3 year range for immunization.

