#### Safety evaluation

The primary end point for evaluating safety will be defined as the occurrence of any of the following diarrhoea, vomiting or abdominal cramps of at least moderate grade. Diarrhea will be defined as three or more loose or liquid stools in any 24-h period. A measured oral or rectal temperature above 38°C will be considered a fever.

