- 8. Diarrhoea has been defined in the protocol (page 9) and the reaction form (appendix V) modified as well.
- 9. Results from children taking only one dose of the vaccine will also be used for data analysis. Those children who are not able to take a second dose of the vaccine due to fever or diarrhoea will be excluded from the study and not be given a dose later.
- 10. A positive response will be defined in terms of a two fold increase over the individuals baseline value. Only ASC levels > 10 ASCs per 10^7 MNCs in the post immunization specimen will be considered a responder.

| cipal Investigator: Last, first, middle |
|---|
|---|

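### The stool-count line on all six reaction forms is marked more than 3, but the protocol and the forms' own footnote define diarrhoea, a primary safety component, as 3 or more

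*Protocol*

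**What the plan says.** The protocol's Safety evaluation section defines the primary safety endpoint as the "occurrence of any of the following diarrhoea, vomiting or abdominal cramps of at least moderate grade". It then fixes the diarrhoea component: "Diarrhea will be defined as three or more loose or liquid stools in any 24-h period". The exclusion criterion on recent diarrhoea in Selection of study subjects uses the same threshold of three.

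Safety Monitoring of the Vaccine names the Appendix V forms as the place where all side-effects are recorded. They are completed from daily home interviews on the three days after each dose, so there are six forms (days 1 to 3 after the primary and after the secondary vaccination). On each of them, item 2.0 Local reaction contains:

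- a footnote: "Diarrhoea defined as passing of ≥ 3 loose or liquid stools per day";
- a stool-count line, which on the form for day 1 after the secondary vaccination reads "If yes above number/day (> 3"), with the same sign on the other five;
- one No/Yes code for the block holding 'Other symptoms' and diarrhoea. On two forms the text reads "Other symptoms *Diarrhoea [watery stool or loose stool] | 1=No 2= Yes".

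In Response to comments of reviewers (Reviewer 2, item 8) the investigators state: "Diarrhoea has been defined in the protocol (page 9) and the reaction form (appendix V) modified as well".

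**The concern.** The forms are the source record for a component of the primary safety endpoint, and they carry two thresholds for it on the same sheet. Three stools in a day is the smallest count that qualifies under the protocol, and it is the one count on which the two thresholds disagree. The stated purpose of modifying the form was to bring it into line with the definition. The footnote does so and the count line does not.

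The apparently shared code adds to the problem. With a code of its own, diarrhoea could be read from the Yes alone and the count label would matter little. If the code is shared with other local symptoms, the count is what tells the analyst that a Yes means diarrhoea, and that is the field with the conflicting threshold.

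At stake is consistent scoring of threshold cases, both in the composite and in the comparison of diarrhoea as an individual symptom, which Data analysis assigns to Fisher's exact test.

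**Working it through.** No figure in the protocol depends on this, so the check is a comparison of texts.

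**Step 1. Does exactly 3 loose stools in a day qualify?**

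| Place in the protocol | Rule | Does 3 meet it? |
|---|---|---|
| Safety evaluation | ≥ 3 in 24 h | yes |
| Selection of study subjects, exclusion (b) | ≥ 3 in 24 h | yes |
| Appendix V footnote, six of six forms | ≥ 3 per day | yes |
| Appendix V count line, six of six forms | > 3 | no |

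Counts of 4 or more meet every rule, and counts of 0 to 2 meet none. The conflict is confined to a count of 3.

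**Step 2. How is the code laid out?** On the forms for days 1 and 2 after the secondary vaccination, 'Other symptoms' and diarrhoea stand in one cell with one No/Yes code. On the other four forms the code stands on the 'Other symptoms' line, and the line beginning "Diarrhoea [watery stool" has an empty answer column. No form shows a second code for diarrhoea. All six are consistent with one code for the block, but the two renderings differ, so the text at hand does not settle the printed layout.

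**Step 3. What could be recorded?**

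| Child on that day | Worker follows the footnote | Worker follows the count label |
|---|---|---|
| 4 or more loose stools | Yes, count entered | Yes, count entered |
| exactly 3 loose stools | Yes, count 3 | Yes, count possibly blank |
| other local symptom only, if the code is shared | Yes, no count | Yes, no count |

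Under the footnote, a child with 3 stools is identifiable. Under the count label, the same child may yield a bare Yes. If the code is shared, that record cannot be told apart from the one in the last row.

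**The case against.** **Reading error.** The tables were read by a program, and a ≥ can lose its underline. On one form the ≥ in the completeness-of-dosing item is itself garbled, and the ASC responder rule appears with ≥ in one section and > in another. The six forms share one template, so six repeats are not six independent confirmations. This cannot be excluded without the printed page. Against it, the ≥ in the footnote reads correctly on all six forms while the count line reads > on all six. The mismatch therefore stands as the best reading of the text.

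**'Other symptoms' may be a heading.** The block has no space to specify another local symptom, the count line makes sense only for stools, and item 3.0 has its own coded 'Other' row. If so, the code belongs to diarrhoea alone, the footnote defines a Yes, and a child with 3 stools is scored correctly without the count. The form does not say this, but the reading is plausible, so the shared code is only an apparent fault.

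**Safeguards.** Nothing tells the worker to leave the count blank at 3. Data management provides for review of the forms and for further home visits to complete missing entries, and 5% of subjects are re-interviewed within a day. These could catch a Yes without a count, though a reviewer who follows the > 3 label may not see a gap.

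**A stronger reading.** A reader might infer that children with exactly 3 stools are lost to the endpoint, so that the event rate and the power fall by a calculable amount. The documents do not support this. They give no distribution of stool counts. The endpoint is a composite observed over three days per dose, so a child with 3 stools on one day may still qualify through another day, vomiting or cramps. Data analysis assigns the profile likelihood method, not Fisher's test, to the primary outcomes and also analyses the two age groups together. A power loss worked out for Fisher's test in a single age group would not describe the planned analysis.

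**Conclusion.** The contradiction in threshold holds: all six forms mark the stool count as more than 3, against 3 or more in their own footnote and in Safety evaluation. It concerns a component of the primary safety endpoint on the form named as its record. The consequence is possible inconsistent recording of children with exactly 3 loose stools in a day. Certain loss or a demonstrated bias does not follow, and the size of any effect cannot be derived from the documents.

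The conclusion assumes that the > on the count line is as printed. The shared code is a secondary point that holds only if the printed form matches the text at hand. If the printed form gives diarrhoea its own code, the label mismatch remains but matters less.

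**What to change.** On all six Appendix V forms:

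1. Change the count label from > 3 to ≥ 3, to agree with Safety evaluation and the footnote. Alternatively, drop the threshold from the label and record the number of loose or liquid stools whenever any are reported, so that the definition is applied at analysis and not at the interview.
2. Check the printed layout. If diarrhoea and 'Other symptoms' do share a code, give diarrhoea its own row and No/Yes code.
3. State that the diarrhoea component is derived from the recorded count using the Safety evaluation definition.

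The cost is reprinting one row of the form before enrolment, with no additional subjects or visits. The change is best made before enrolment because the data are 24-hour recall, and an ambiguous record may be hard to resolve later.

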#### 3.0 SYSTEMIC REACTION

| Parameters               |              |
|--------------------------|--------------|
| Fever (oral or rectal    | 1= No 2= Yes |
| temp>37.8°C              |              |
| If yes, temperature (°C) |              |
| Loss of appetite/Poor    | 1= No 2= Yes |
| feeding                  |              |
| Irritability             | 1= No 2= Yes |
| Nausea                   | 1= No 2= Yes |
| Dizziness                | 1= No 2= Yes |
| Exanthema                | 1= No 2= Yes |
| Other                    | 1= No 2= Yes |

#### 4.0 Relation to vaccine

1= None 2= Possible 3= Probable 4= Highly probable

#### 5.0 Therapy required

1= No 2= Yes

#### 6.0 Outcome

#### **AppendixV**

#### Adverse event form

### Surveillance after Secondary vaccination Day 2

1.0 Completeness of dosing. Amount ingested: 1=100% 2=≥90% 3=<90%

#### 2.0 LOCAL REACTION

| Parameters  |                                   |
|---|-----------------------------------|
| Abdominal pain  | 1= No 2=Mild 3= moderate 4=severe |
| Cramp   | 1= No 2= Yes                      |
| Distension  | 1=No 2= moderate 3= severe        |
| Vomiting  | 1=No 2= Yes                       |
| If yes, number/day                                      |                                   |
| Other symptoms *Diarrhoea [watery stool or loose stool] | 1=No 2= Yes                       |
| If yes above number/day (> 3)                           |                                   |

\*Diarrhoea defined as passing of ≥ 3 loose or liquid stools per day

#### 3.0 SYSTEMIC REACTION

| Parameters  |              |
|---|--------------|
| Fever (oral or rectal temp>37.8°C  If yes, temperature (°C) | 1= No 2= Yes |
| Loss of appetite/ Poor feeding                              | 1= No 2= Yes |
| Irritability  | 1= No 2= Yes |
| Nausea  | 1= No 2= Yes |
| Dizziness   | 1= No 2= Yes |
| Exanthema   | 1= No 2= Yes |
| Other   | 1= No 2= Yes |

#### 4.0 Relation to vaccine

1= None 2= Possible 3= Probable 4= Highly probable

#### 5.0 Therapy required

6.0 Outcome

#### Appendix V

## Adverse event form Surveillance after Secondary vaccination

Day 3

1.0 Completeness of dosing. Amount ingested: 1=100%  $2=\ge 90\%$  3=<90%

#### 2.0 LOCAL REACTION

| Parameters               |                                   |
|--------------------------|-----------------------------------|
| Abdominal pain           | 1= No 2=Mild 3= moderate 4=severe |
| Cramp                    | 1= No 2= Yes                      |
| Distension               | 1=No 2= moderate 3= severe        |
| Vomiting                 | 1=No 2= Yes                       |
| If yes, number/day       |                                   |
| Other symptoms           | 1=No 2= Yes                       |
| *Diarrhoea [watery stool |                                   |
| or loose stool ]         |                                   |
| If yes above number/day  |                                   |
| (>3)                     |                                   |

\*Diarrhoea defined as passing of ≥ 3 loose or liquid stools per day

#### 3.0 SYSTEMIC REACTION

| Parameters                        |              |
|-----------------------------------|--------------|
| Fever (oral or rectal temp>37.8°C | 1= No 2= Yes |
| If yes, temperature (°C)          |              |
| Loss of appetite/ Poor            | 1= No 2= Yes |
| feeding                           |              |
| Irritability                      | 1= No 2= Yes |
| Nausea                            | 1= No 2= Yes |
| Dizziness                         | 1= No 2= Yes |
| Exanthema                         | 1= No 2= Yes |
| Other                             | 1= No 2= Yes |

#### 4.0 Relation to vaccine

1= None 2= Possible 3= Probable 4= Highly probable

#### 5.0 Therapy required

1= No 2= Yes

#### 6.0 Outcome

| Principal Investigator: Last, | first, midd | lle |
|-------------------------------|-------------|-----|
|-------------------------------|-------------|-----|

#### **Detailed Budget for New Proposal**

Project Title: Phase II Safety and immunogenicity studies of the enterotoxigenic *Escherichia coli* (ETEC) vaccine

Name of PI: [name], ICDDR,Ba

Protocol Number: Name of Division: Laboratory Sciences Division

Funding Source: USAID Amount Funded (direct): US\$ 96,957 Total:US\$121,196

Overhead (25%) 24,239

Starting Date ASAP:

Closing Date: Two years from starting date

Strategic Plan Priority Code(s): Diarrhoeal disease/ Child Health Research

| Sl. No      | Account Description   | Salary Support              |         | US \$ Amount Requested |                    |                    |                    |
|-------------|---|-----------------------------|---------|------------------------|--------------------|--------------------|--------------------|
| <del></del> | Personnel   | Position                    | Effort% | Salary                 | 1 st Yr | 2 nd Yr | 3 rd Yr |
|             | [name]  | Senior Scientist            | 25      |                        | 6,150              | 7,380              |                    |
|             |   | Medical Officer             | 100     |                        | 5,640              | <del>-</del>       |                    |
|             |   | Medical officer             | 5       |                        | 605                |                    |                    |
|             |   | Research Officers (2)       | 100     |                        | 6168               | 6476               |                    |
|             |   | Laboratory
Attendant (1) | 100     |                        | 1,985              | 2,095              |                    |
|             |   | Health workers(3)           | 100     |                        | 2,808              | 0                  |                    |
|             |   | Sub Total                   |         |                        | 23,356             | 15,951             |                    |
|             | Consultants   |                             |         |                        |                    |                    |                    |
|             | Local Travel  |                             |         |                        | 2000               | 500                |                    |
|             | International Travel  |                             |         |                        |                    |                    |                    |
|             |   | Sub total                   |         |                        | 2,000              | 500                |                    |
|             |   |                             |         |                        |                    |                    |                    |
|             | Supplies and Materials (Descr                                 | iption of Items)            |         |                        | •••••              |                    |                    |
|             | Immunoreagents, antibodies,
ELISA plates, pipettes, ELISPO |                             |         | astics,                | 15,000             | 15,000             |                    |
|             | Sub Totals  | or and other supplies,      | CIC.    |                        | 12,000             | 15,000             |                    |

Principal Investigator: Last, first, middle

| Other Contractual Services      | }     |       |
|---------------------------------|-------|-------|
| Repair and Maintenance          | 1000  | 2000  |
| Rent, Communications, Utilities | 850   | 500   |
| Training Workshop, Seminars     | 500   | 100   |
| Printing and Publication        | 1,000 | 1,000 |
|                                 |       |       |

| Interdepartmental Services  | 1st Yr         | 2 nd Yr | 3 rd Yr |
|---|----------------|--------------------|--------------------|
| 
Computer Charges  | 150            | 150                |                    |
| Pathological Tests  | 1500           | 100                |                    |
| Microbiological tests   | 1,500          | 500                |                    |
| Biochemistry Tests  |                |                    |                    |
| Hospitalization charges   | 1500           |                    |                    |
| Biochemistry and Nutrition  | 500            |                    |                    |
| Sub Totals  | 5150           | 750                |                    |
| Computer for laboratory Capital Expenditure ELISA READER and computer programme for first year, replacement of micropipettes etc. for second year | 3500
10,000 | 1800               |                    |

 DIRECT COST
 59,356
 37,601

 INDIRECT COST
 14,839
 9,400

 TOTAL COST
 121,196
 74,195
 47,001

| Principal Investigator: Last, first, middle |
|---|
|---|

